2.4.4 Secondary effectiveness analysis

The percentage of responders based on the MMVS on both sides of the face concurrently will also be derived at all applicable follow-up visits for both the blinded evaluator's assessment and the treating investigator's assessment respectively. The response rates and their 95% confidence interval will be presented by visit and group.

Fisher's exact test will be used to compare the response rates in the Treatment group versus the Control group based on the blinded evaluator's assessment and the treating investigator's assessment respectively. In other words, the null hypothesis

$H_0: \pi_{t,Sculptra} = \pi_{t, Control}$ will be tested against the alternative hypothesis

$H_1: \pi_{t,Sculptra} \neq \pi_{t, Control}$ for each of the timepoints $t =$ Month 6 and Month 9 for the blinded evaluator's assessment, and $t =$ Month 6, Month 9 and Month 12 for the treating investigator's assessment.

The volume change in the midface area as compared with baseline (right and left sides combined) obtained by 3D imaging will be presented descriptively by treatment for all applicable follow-up visits.

GAIS (by treating investigator and subject) and satisfaction with the treatment outcome will be analyzed descriptively.

2.5 Safety Analysis

For Group B all safety variables will be summarized descriptively based on the safety population. For Group A all safety variables will be summarized descriptively based on all subjects.

2.5.1 Extent of exposure

Data of extent of exposure and treatment procedure will be summarized per treatment session and also in total. Other relevant injection parameters, such as injection depth, injection method will be presented in a similar way.

 GALDERMA	Title 43CHSA1803 Statistical Analysis Plan - Sculptra China	Doc id MA-40407
--	---	---------------------------

2.5.2 Subjects Diary

Number and percentage of subjects reporting anticipated injection related reactions, as collected in diaries will be presented in total and by maximum intensity for each treatment session (only Sculptra treated subjects). Graphs will be generated to illustrate the incidence over time. Number of days with the event will be summarized using mean, SD, min, max and median.

2.5.3 Adverse events

All AEs will be coded according to MedDRA.

A summary of all AEs, by Treatment Group, will be provided, which will include:

- Number of subjects with at least one AE and number of events (in total as well as serious AEs)
- Number of subjects with at least one related AE and number of events (in total as well as serious AEs)
- Number of subjects with at least one unrelated AE and number of events (in total as well as serious AEs)
- Number of subjects who did not have an AE.

Related AEs as well as number of subjects with related AEs will be summarised by SOC, PT and intensity. In addition, for related AEs the number of days to onset and the duration of event will be summarised by SOC and PT using mean, SD, min, max and median. Action taken for related AEs will also be summarized. Related AEs will be summarized per treatment session.

Serious AEs will be listed.

Late onset (>21 days) AEs will be listed.

Related AEs with late onset (>21 days after most recent treatment) will be listed, if any.

Non-related AEs will be summarised by SOC, PT, and intensity and by Treatment Group.

Time to onset of an AE will be derived as the start date minus the date of most recent treatment. For the Control group date of randomization will be used instead of most recent treatment. If the start date is missing, it will be assumed that the AE started on the day of most recent treatment. If the start month is available but not the day, it will be assumed that the AE started on the first day of the month.

Duration of an AE will be derived as the stop date minus the start date + 1. If the start date is missing, it will be assumed that the AE started on the day of most recent treatment or date of randomization for the Control group. If the start month is available but not the day, it will be assumed that the AE started on the first day of the month. If the stop month is available but not the day, it will be assumed that the AE stopped on the last day of the month. Completely missing stop dates will not be imputed and therefore no duration will be calculated in these cases. Instead, the number of AEs that were ongoing at the end of the study will be given.

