**Effective**

Version: 2.0

	
blinded evaluator's assessment and the treating investigator's assessment respectively. The response rates and their 95% confidence interval will be presented by visit and group.
 
Fisher's exact test will be used to compare the response rates at Month 6 and 9 based on the blinded evaluator's assessment. For response rates based on the treating investigator's assessment, response rates will be compared at Month 6, 9 and 12 using Fisher's exact test.
 
The volume change in the midface area as compared with baseline (right and left sides combined) obtained by 3D imaging will be presented by treatment for all applicable follow-up visits.
 
GAIS (by treating investigator and subject) and satisfaction with the treatment outcome will be analyzed descriptively.
 
Safety
 
Anticipated injection related reactions, as collected in Treatment Group, as collected in 4-week diaries after each treatment session, will be summarized using frequency tables. Adverse event incidences will be summarized by MedDRA system organ class (SOC) and preferred term (PT).
 
Sample size
 
There are no available clinical data for Sculptra studied under conditions similar to the current study. However, based on what is seen in clinical studies of injectable fillers in the facial areas, it is reasonable to assume a response rate of at least 60% in the Sculptra Treatment Group at Month 12. For the no treatment Control Group, response rate of 25.8% has been observed in an ongoing clinical trial in China. Based on this, it was assumed that the response rate will be maximum 30% in the no-treatment Control Group at Month 12.
 
With a sample size of 100 subjects treated with Sculptra and 50 subjects in the no-treatment control group, Fisher's Exact test will have approximately 90% power to detect difference between the anticipated percentage of responders at a 5% significance level (two-sided). To account for 20% drop-outs, approximately 126 will be randomized to the Sculptra group and approximately 63 to the control group.

--	---

 GALDERMA	Title 43CHSA1803 Clinical Study Protocol	Doc id MA-39381
---	--	---------------------------

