#### 4.4.2 Blinding

Only the evaluator will be blinded, both treating investigator and subjects will be open-labelled.

The Blinded Evaluator shall not be allowed to retrieve study supplies or to be present during opening of the study supplies or injections. The Treating Investigator is not allowed to discuss treatments with the blinded evaluator or the subjects. All documents with information on study products shall be kept in a separate binder not available to the blinded evaluator.

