## 10.5 Safety Analysis

Number and percentage of subjects reporting anticipated injection related reactions, as collected in diaries will be presented in total and by maximum intensity. A graph will be generated to illustrate the incidence over time. Number of days with the event will be summarized using mean, SD, min, max and median.

All AEs will be coded according to MedDRA.

A summary of all AEs, by treatment, will be provided, which will include:

- Number of subjects with at least one AE and number of events (in total as well as serious AEs)
- Number of subjects with at least one related AE and number of events (in total as well as serious AEs)
- Number of subjects with at least one unrelated AE and number of events (in total as well as serious AEs)
- Number of subjects who did not have an AE.

Related AEs as well as number of subjects with related AEs will be summarised by SOC, PT and intensity and by treatment. In addition, for related AEs the number of days to onset and the duration of event will be summarised by SOC and PT and treatment using mean, SD, min, max and median. Action taken for related AEs will also be summarized.

Serious AEs will be listed.

Non-related AEs will be summarised by SOC, PT, and intensity and by treatment.

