1.6 Safety endpoints

- Incidence, intensity, duration, and onset of adverse events (AEs) collected throughout the study.
- Incidence, intensity, and number of days of anticipated injection related reactions, collected using 4-week subject diaries after each treatment session for the Treatment Group.

Effective

Version: 1.0

	Title 43CHSA1803 Statistical Analysis Plan - Sculptra China	Doc id MA-40407
--	---	---------------------------

Effective date: 2019-10-24 08:59

Effective

Version: 1.0

2 Statistical Methods

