		n (%)	Serial Puncture	

2019-10-24 08:59

Effective date:

Effective

Version: 1.0

Characteristic	Visit	Statistic	Answer	Result
		n (%)	Fanning	
		n (%)	Other	
	Treatment 4 (optional)	n (%)	Linear Retrograde	
		n (%)	Serial Puncture	
		n (%)	Fanning	
		n (%)	Other	
Post-treatment care (ice and massage) according to study protocol?	Baseline / Treatment 1	n (%)	Yes	
		n (%)	No	
	Treatment 2 (optional)	n (%)	Yes	
		n (%)	No	
	Treatment 3 (optional)	n (%)	Yes	
		n (%)	No	
	Treatment 4 (optional)	n (%)	Yes	
		n (%)	No	
Any deviation from the treatment procedure as described in the study protocol?	Baseline / Treatment 1	n (%)	Yes	
		n (%)	No	
	Treatment 2 (optional)	n (%)	Yes	
		n (%)	No	
	Treatment 3 (optional)	n (%)	Yes	
		n (%)	No	
	Treatment 4 (optional)	n (%)	Yes	
		n (%)	No	

List deviations:...

2019-10-24 08:59

Effective date:

Effective

Version: 1.0

Safety**Table 3-42: Anticipated injection related reactions recorded in the subject diary after first treatment (both sides of the face combined), Safety population**

Event	Treatment with Sculptra N=XX							
	Subjects		Maximum intensity					
			Mild		Moderate		Severe	
	n	%	n	%	n	%	n	%
Pain								
Tenderness								
Localized redness								
Bruising								
Hematoma								
Edema								
Other								
No diary events								

 $\% = (n/N)*100$

Note: Percentages for intensity categories are based on the number of subjects reporting the symptom.

Table 3-43: Number of days anticipated injection related reactions recorded in subject diary after first treatment (both sides of the face combined), Safety population

Event	Treatment with Sculptra N=XX					
	n	Mean	SD	Minimum	Median	Maximum
Pain						
Tenderness						
Localized redness						
Bruising						
Hematoma						
Edema						
Other						

Figure 3-5: Proportion of subjects with observed anticipated injection related reactions (to any intensity level) after first treatment with Sculptra (both sides of the face combined), Safety population

Same tables and figure for treatment sessions two, three and four

 GALDERMA	Title 43CHSA1803 Statistical Analysis Plan - Sculptra China	Doc id MA-40407
--	---	---------------------------

Effective date: 2019-10-24 08:59

Table 3-44: Brief summary of all AEs, Main study, Safety population

	Sculptra, N=XX			Control, N=YY		
	Subjects		Events	Subjects		Events
	n	%	#	n	%	#
Adverse Events reported, total						
Total, serious						
Total, non-serious						
AEs related to injection procedure and/or product, total						

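### No by-term adverse-event comparison between the arms is planned that does not depend on the open-label causality call

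*SAP*

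**What the plan says.** The safety endpoint in SAP 1.6 is "Incidence, intensity, duration, and onset of adverse events (AEs) collected throughout the study", with no restriction to related events. The protocol synopsis (Statistical Methods, Safety) is equally general: "Adverse event incidences will be summarized by MedDRA system organ class (SOC) and preferred term (PT").

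The detailed sections are narrower. Protocol 10.5 says "Related AEs as well as number of subjects with related AEs will be summarised by SOC, PT and intensity and by treatment" and "Non-related AEs will be summarised by SOC, PT, and intensity and by treatment". SAP 2.5.3 keeps the split. For unrelated events it says "Non-related AEs will be summarised by SOC, PT, and intensity and by Treatment Group". For related events it says "Related AEs as well as number of subjects with related AEs will be summarised by SOC, PT and intensity", and the sentence ends there, without the by-treatment display that protocol 10.5 has. SAP 2.1 gives the SAP precedence over the protocol's statistical sections where they differ.

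Under SAP 1.5 the treating investigator answers two causality questions, one on the product and one on the injection procedure. A yes to either makes the event related. The sponsor reviews the call, and a disagreement is settled as related. On blinding, protocol 4.4.2 says "Only the evaluator will be blinded, both treating investigator and subjects will be open-labelled".

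**The concern.** In a trial with an untreated control arm, the plainest safety question for any term is how many subjects in each arm had it, whatever the cause. Answering it needs no judgement about causality. The planned tables never give that answer by term, because each one first sorts events by an opinion formed with knowledge of the arm.

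The sorting does not act equally on the two arms. Both causality questions concern things that Control subjects do not receive, so a Control event can hardly be called related. A Sculptra event can be, and the rule for sponsor disagreement moves events in that direction only. The unrelated-events tables thus set a filtered Sculptra arm beside an almost unfiltered Control arm. Someone who compares the two could miss an excess on Sculptra, or see a deficit that is not there.

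**Working it through.** The plan gives no figure on this point to reproduce. The check has two parts: a count of the table shells, and arithmetic on the consequence.

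**1. Adverse-event table shells in SAP Section 3, main phase**

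| Table | Events | Arms | SOC/PT rows |
|---|---|---|---|
| 3-44 | all | both | no |
| 3-45 to 3-49 | related | Sculptra only | yes (3-47 to 3-49 by PT) |
| 3-50 | unrelated | Sculptra | yes |
| 3-51 | unrelated | Control | yes |

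The first row is "Table 3-44: Brief summary of all AEs, Main study, Safety population", which holds totals only. Seven tables have term rows, and all seven are conditioned on relatedness. None shows all events by term. The extension and combined phases reuse the same shells, so they add no such table.

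**2. Bias of the unrelated-only contrast**

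Inputs: planned arm sizes of 126 and 63 (SAP 2.7). Assumptions, not from the documents: each affected subject has one event of the term; no Control event is called related; a share q of affected Sculptra subjects have theirs called related. Let t and c be the true all-cause proportions in Sculptra and Control.

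- All-cause difference: t − c
- Difference between Tables 3-50 and 3-51: t(1 − q) − c
- Bias: −t × q, which is zero or negative and so never against Sculptra

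| t | c | True difference | q = 0 | q = 25% | q = 50% | q = 75% |
|---|---|---|---|---|---|---|
| 10% | 10% | 0 | 0 | −2.5 | −5 | −7.5 |
| 20% | 5% | +15 | +15 | +10 | +5 | 0 |

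(Differences in percentage points.) In counts, for t = c = 10% and q = 50%: 12.6 of 126 Sculptra subjects are expected to have the term, but 6.3 of 126 (5%) appear in Table 3-50, against 6.3 of 63 (10%) in Table 3-51.

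**3. Can the all-cause figure be rebuilt from the tables?**

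Event counts can: for Sculptra, add Tables 3-45 and 3-50. Subject counts cannot, because one subject may have a related and an unrelated event under the same term. The number of subjects with the term satisfies

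max(n_rel, n_unrel) ≤ n_all ≤ n_rel + n_unrel.

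For assumed counts of 10 related and 8 unrelated subjects, n_all lies between 10 and 18, so incidence lies between 10/126 = 7.9% and 18/126 = 14.3%. The same overlap prevents rebuilding maximum intensity per subject.

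**The case against.** The strongest reply is that little is hidden. Related events have the fullest display in the SAP: by term and intensity, by session, with onset, duration and action taken. A reader can set Table 3-45 beside Table 3-50 and bound the Sculptra incidence. Table 3-51 is in effect all Control events, and Table 3-44 has a Control column that would reveal any related ones. Serious and late-onset events are listed without a relatedness filter, and SAP 2.1 puts all data in subject listings. Safety is descriptive, with no hypothesis test. All of this stands, and it limits the point to the missing tabulation. It does not remove the point: bounds are not an incidence, and listings are not a planned summary.

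The reply also rules out several stronger readings that a reader might infer:

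- *That no by-term comparison of the arms is planned.* One is, for unrelated events, in Tables 3-50 and 3-51. What is missing is one free of the causality call.
- *That the SAP alone breaks a protocol promise.* Protocol 10.5 has the same split. The synopsis sentence says neither that causality is ignored nor that arms are compared. The SAP's own departure is dropping the by-treatment display for related events.
- *That the events which differ between arms disappear.* They appear in Table 3-45, so the unrelated-only contrast must not be taken as all that a reader would see.
- *That the endpoint obliges onset and duration summaries for all events.* SAP 1.6 names onset and duration but prescribes no summary, and protocol 10.5 asks for them for related events only.

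**Conclusion.** The point holds as a gap in the planned safety tables. No by-term comparison independent of an open-label judgement is planned, and the one by-term arm contrast that is planned leans towards Sculptra. Under the stated assumptions the lean equals t × q: 5 points at a 10% incidence with half of the cases called related, and 15 points at 20% with three quarters called related. It is zero if no Sculptra case of the term is called related. It is smaller where a subject has both kinds of event, since that subject stays in Table 3-50. That Control events are nearly all called unrelated is an inference from the wording of the causality questions and the lack of any treatment in that arm; the documents do not state it.

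An all-cause table would not be a strictly randomised comparison either. SAP 2.2 defines the Safety population as treated, and untreated subjects randomised to Sculptra are outside it. It would still be free of the causality call. The primary effectiveness analysis, data collection and trial conduct are unaffected.

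**What to change.** Add to SAP 2.5.3 and Section 3 one main-phase table of all adverse events regardless of causality, by SOC, PT and maximum intensity. Give subjects n (%) and number of events, with Sculptra and Control side by side, on the Safety population. Restore the by-treatment display for related events, as in protocol 10.5, even if the Control column proves empty. Keep Tables 3-45, 3-50 and 3-51 as subsets of the new table.

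The cost is one or two extra descriptive tables from events that are already to be MedDRA-coded. No change to conduct or data collection is needed. SAP 2.1 provides for amendment before database lock. It also lets supportive analyses be added later without one, but specifying the table in advance is cleaner.

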#### Treatment

Each subject assigned to Group A and Treatment Group will receive up to 4 injection sessions with 5( $\pm 1$ ) weeks (at least 4 weeks) intervals. Initial treatment will be on Day 1. Study treatments should be stopped if optimal midface augmentation has been obtained or a maximum of 4 injection sessions completed. Optimal midface augmentation is defined as the best possible aesthetic result that can be obtained for an individual study participant, as agreed upon by the treating investigator and subject.

Subjects assigned to the Control Group will not receive treatment during the study.

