#### 4.7 Schedule of events

**Table 1. Schedule of Events for Group A and Treatment Group**

	Screening	Baseline / Treatment 1	Treatment 2 (Optional) b	Treatment 3 (Optional) b	Treatment 4 (Optional) b	Follow-up	Follow-up	Final visit / Early termination
	D-21 to D1	D1	5W( $\pm 1w$ ) after treatment 1	5W( $\pm 1w$ ) after treatment 2	5W( $\pm 1w$ ) after treatment 3	5W( $\pm 1w$ ) after Last treatment	6M ( $\pm 2w$ ), 9M ( $\pm 2w$ ), 12M ( $\pm 2w$ ), and 18M ( $\pm 3w$ ) after Baseline	24M ( $\pm 4w$ ) after Baseline
Informed consent	X							
Demography	X							
Height		X						
Weight		X					X	X
Medical history & concurrent diseases	X	X a						
Concomitant medication/procedures	X	X a	X	X	X	X	X	X
Vital signs		X c						
Laboratory tests	X						X d	X e
Pregnancy test for childbearing potential women	X	X a,c	X c	X c	X c			X
Inclusion and Exclusion criteria	X	X a						
Randomization		X						

Treatment		X	X	X	X			
MMVS (Blinded Evaluator)	X	X a,c					X	X
MMVS (treating investigator)	X	X a,c	X c	X c	X c	X	X	X
Photography		X c	X c	X c	X c	X	X	X
GAIS (Treating investigator and Subject)			X c	X c	X c	X	X	X
Subject satisfaction questionnaire							X	X
Dispense subject diary		X	X	X	X			
Review and collect subject diary			X	X	X	X		
Device deficiencies		X	X	X	X			
Assessment of AE	X	X a	X	X	X	X	X	X
Study termination								X

- a) Omitted if screening and baseline visit occur on the same day.
- b) The visit is omitted if optional treatment was not performed.
- c) Performed prior to treatment.
- d) Only performed at 12M.
- e) Only performed at early termination if termination occurs before 12M visit.

	
Title 43CHSA1803 Clinical Study Protocol
	
Doc id MA-39381

--	--	-----------------------------------

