**Effective**

Version: 2.0

associated with inflammation or discolouration. The early occurrence of subcutaneous nodules at the injection site (within 3–6 weeks after treatment) may be minimised by adhering to proper dilution and injection techniques. Delayed occurrences of subcutaneous nodules at the injection site (within 1–14 months post injection) have been reported with sometimes a prolonged duration of up to 2 years. Improper injection techniques such as superficial placement, excessive amount of product or incorrect reconstitution may lead to appearance of papules or nodules at the injection site. Massaging the treatment area to ensure proper distribution of the product may minimise the appearance of such papules or nodules.

For nodular areas or late granuloma formation, in some cases, they resolved spontaneously or following treatment with multiple intralesional injections of corticosteroids and/or antineoplastic agents (e.g. 5-fluorouracil). Surgical excision of the nodules was sometimes required when they were larger in size, occurring in difficult anatomical regions (e.g. lower eyelid) or persisting after other treatments.

This product must not be injected intramuscularly or intravascularly. Localised superficial necrosis and scarring may occur after injection in or near vessels. It is thought to result from the injury, obstruction, or compromise of blood vessels. Special caution should be taken if the patient has undergone a prior surgical procedure in the planned treatment area. Areas with limited collateral blood flow has an increased risk of ischaemia. Aspiration prior to injection is recommended.

Unintentional introduction of soft tissue fillers into the vasculature in the face may lead to embolisation, occlusion of the vessels, ischaemia, necrosis or infarction at the implant site or in the area supplied by the blood vessels affected. Rare but serious adverse events include temporary or permanent vision impairment, blindness, cerebral ischaemia or cerebral haemorrhage leading to stroke, skin necrosis, and damage to underlying facial structures. Immediately stop the injection if any of the following symptoms occurs, including changes in vision, signs of a stroke, blanching of the skin, or unusual pain during or shortly after the procedure. Patients should receive prompt medical attention and possibly evaluation by an appropriate health care practitioner specialist, should an intravascular injection occur.

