1.1 Background

1.1.1 Study design

This is a randomized, multi-center, evaluator-blinded, no-treatment controlled study of Sculptra for correction of Midface Volume Deficit and/or Midface Contour Deficiency in subjects of Chinese origin, men or women aged 18 years or older.

For Group A, after screening, eligible subjects will be treated from day 1 and followed up for 24 months.

For Group B, the study includes two phases as follows:

Main study phase: It is randomized, evaluator-blinded and no-treatment controlled. After screening, all eligible subjects will be randomized either to the Treatment Group or the Control Group in a 2:1 ratio. All the subjects will be followed up for 12 months.

Extension study phase: After the main study phase, the Treatment Group and Group A will be followed up for additional 12 months.

Each Treating Investigator will enroll 1 or 2 subjects as Group A. Before start of enrolment into Group B, the injection technique will be evaluated by the Sponsor or designee of Sponsor and performed after the subjects in Group A for each investigator have received their first treatment and second treatment. If treatments are found to be correctly performed, no further training is needed, there are no outstanding questions regarding the injection technique and no other corrective actions are identified, the enrolment in Group B can start for that investigator.

Each subject assigned to Group A and Treatment Group will receive up to 4 injection sessions with 5 (± 1) weeks intervals. Study treatments should be stopped if optimal midface augmentation has been obtained or a maximum of 4 injection sessions completed. Optimal midface augmentation is defined as the best possible aesthetic result that can be obtained for an individual study participant, as agreed upon by the treating investigator and subject.

Subjects assigned to the Control Group will not receive treatment during the study.

For more details regarding the study, and references, see the Clinical Study Protocol (MA-39381).

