Serious						
Non-serious						
Unrelated AEs, total						
Serious						
Non-serious						
Subjects with no AE reported						

$$\% = (n/N) * 100$$
Table 3-45: Related Adverse Events by MedDRA SOC and preferred term, Main study, subjects randomized to Sculptra, Safety population

Primary SOC	Preferred Term	Subjects		Events	Maximal Intensity		
		n	%		Mild	Moderate	Severe
Total							

$$\% = (n/number of subjects in the Safety population) * 100$$
Effective

Version: 1.0

	Title 43CHSA1803 Statistical Analysis Plan - Sculptra China	Doc id MA-40407
--	---	---------------------------

**Table 3-46: Related Adverse Events by MedDRA SOC and preferred term, by treatment session,
Main study, subjects randomized to Sculptra, Safety population**

Visit	Primary SOC	Preferred Term	Subjects		Events #	Maximal Intensity		
			n	%		Mild	Moderate	Severe
Baseline / Treatment 1								
Treatment 2 (optional)								
Treatment 3 (optional)								
Treatment 4 (optional)								

% = (n/number of subjects in the Safety population)*100

2019-10-24 08:59

Effective date:

Effective

Version: 1.0

**Table 3-47: Time to onset from last treatment of related AEs,
Main study, subjects randomized to Sculptra, Safety population**

Preferred term	Time to onset (days)					
	n	Mean	SD	Min	Median	Max
Total						

NA = Not Applicable

**Table 3-48: Duration of related AEs,
Main study, subjects randomized to Sculptra, Safety population**

Preferred term	Duration (days)					
	n	Mean	SD	Min	Median	Max
Total						

NA = Not Applicable

**Table 3-49: Action taken of related AEs,
Main study, subjects randomized to Sculptra, Safety population**

Preferred term	Action taken			
	None	Medication treatment	Non-pharmacological treatment or other procedures / tests	Withdrawn
Total				

**Table 3-50: Unrelated Adverse Events by MedDRA SOC and preferred term,
Main study, Subjects randomized to Sculptra, Safety population**

Primary SOC	Preferred Term	Subjects		Events #	Maximal Intensity		
		n	%		Mild	Moderate	Severe
Total							

% = (n/number of subjects in the Safety population)*100

 GALDERMA	Title 43CHSA1803 Statistical Analysis Plan - Sculptra China	Doc id MA-40407
--	---	---------------------------

2019-10-24 08:59

Effective date:

**Table 3-51: Unrelated Adverse Events by MedDRA SOC and preferred term,
Main study, Subjects randomized to no-treatment control, Safety population**

Primary SOC	Preferred Term	Subjects		Events #	Maximal Intensity		
		n	%		Mild	Moderate	Severe
Total							

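### Per-session percentages of related AEs (SAP 2.5.3, Table 3-46) cannot be compared across sessions: observation time per session is unequal and the denominator is not the subjects injected at that session

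*SAP*

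**What the plan says.** - SAP 2.5.3: "Related AEs will be summarized per treatment session". The shell is Table 3-46, "Related Adverse Events by MedDRA SOC and preferred term, by treatment session", with one block for each of Treatments 1 to 4. Its footnote takes the percentage over the number of subjects in the Safety population, for every block.
- SAP 2.5.3 gives no rule for placing an AE under a session. The nearest is: "Time to onset of an AE will be derived as the start date minus the date of most recent treatment". The same anchor is used for a missing start date and for the list of late-onset related AEs (more than 21 days after the most recent treatment).
- SAP 1.1.1: subjects receive "up to 4 injection sessions with 5 (± 1) weeks intervals", and "Study treatments should be stopped if optimal midface augmentation has been obtained or a maximum of 4 injection sessions completed". Protocol 4.1 sets a minimum interval of 4 weeks. Sessions 2 to 4 are optional; Protocol Table 1 notes: "The visit is omitted if optional treatment was not performed".
- Month 12 and Month 24 are timed from baseline (SAP 1.4.2). AEs are collected to the last scheduled visit (Protocol 8.3.4). The AE tables are repeated, where applicable, for the extension and combined phases (end of SAP section 3).
- Protocol 8.3.8: "Delayed occurrences of subcutaneous nodules at the injection site (within 1–14 months post injection) have been reported".

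**The concern.** A reader will look at Table 3-46 to see whether related events become more or less frequent as injections are repeated. That needs comparable observation time and the right denominator in each block, and the plan provides neither.

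The observation time after a session depends on whether another session follows. The denominator includes subjects who never received the session in question. These two features can pull in opposite directions, so a trend in the table need not reflect the product, and a real trend could be hidden.

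Delayed nodules are the event most exposed to this. A nodule caused by an early session but appearing months later would be booked to the last one. Papules and nodules are recorded as AEs (Protocol 8.3.3) and are not a named diary item, so the per-session diary tables do not replace Table 3-46 for them.

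**Working it through.** The plan states no figure for observation time or AE rate per session, so there is nothing to reproduce. The check has three steps.

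**1. Observation windows under most-recent-treatment assignment.** Inputs: intervals of 4-6 weeks, 1 to 4 sessions, Month 12 = 52 weeks and Month 24 = 104 weeks from baseline. A session followed by another has 4-6 weeks. If session k is a subject's last, its window is 52 (or 104) minus (k-1) × interval:

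| Last session | Weeks to Month 12 | Weeks to Month 24 |
|---|---|---|
| 1 | 52 | 104 |
| 2 | 46-48 | 98-100 |
| 3 | 40-44 | 92-96 |
| 4 | 34-40 | 86-92 |

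A four-session subject at 5-week intervals is observed for 5, 5, 5 and 52 - 15 = 37 weeks. The last window is 37/5 = 7.4 times as long and takes 37/52 = 71% of the year; to Month 24 it is 89/104 = 86%. The last injection falls at week 18 at the latest (3 × 6), so in the extension-phase tables every event would belong to a subject's last session.

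**2. What the table shows with no true session effect.** Each session carries the same acute risk a, and there is a constant late hazard h per week. The risk booked to a session is 1 - (1-a)·exp(-h × window), with a window of 5 weeks if another session follows and 52 - 5(k-1) if not. The documents give neither AE rates nor the share of subjects receiving each session, so these are assumptions: a = 0 or 10%, h = 0.002 or 0.005 per week, several uptake patterns.

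Worked case: a = 10%, h = 0.005, uptake 100/75/50/25%.
- Session 1: 0.75 × [1 - 0.9·exp(-0.025)] + 0.25 × [1 - 0.9·exp(-0.26)] = 0.75 × 12.2% + 0.25 × 30.6% = 16.8%.
- Session 4: 0.25 × [1 - 0.9·exp(-0.185)] = 0.25 × 25.2% = 6.3%.

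Results to Month 12 for a = 10%, h = 0.005 (sessions 1/2/3/4, %). The Safety denominator is taken as the Sculptra subjects; including controls would scale all four figures alike.

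| Subjects receiving sessions 1/2/3/4 (%) | Denominator as in Table 3-46 | Recipients as denominator |
|---|---|---|
| 100/100/100/100 | 12.2/12.2/12.2/25.2 | 12.2/12.2/12.2/25.2 |
| 100/90/70/40 | 14.1/14.3/13.0/10.1 | 14.1/15.9/18.6/25.2 |
| 100/75/50/25 | 16.8/13.3/9.8/6.3 | 16.8/17.8/19.6/25.2 |
| 100/50/25/12.5 | 21.4/10.3/4.9/3.2 | 21.4/20.5/19.6/25.2 |

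The direction also depends on acute risk. With uptake 100/90/70/40, a = 0 and h = 0.005, the Table 3-46 figures rise: 4.5/5.9/6.7/6.8. At h = 0.002 and a = 0 they are 1.9/2.5/2.8/2.9; at h = 0.002 and a = 10% they fall, 11.7/11.2/9.5/6.6.

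To Month 24 with a = 10% and h = 0.005: 12.2/12.2/12.2/42.3 if all have four sessions, and 20.8/17.4/14.0/10.6 for 100/75/50/25.

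**3. Whether the fix removes the artefact.** Recipients as denominator and a common 4-week window give 1 - (1-a)·exp(-4h) for every session: 11.8% (a = 10%, h = 0.005), 10.7% (10%, 0.002), 2.0% (0, 0.005), 0.8% (0, 0.002). Both changes are needed. The right-hand column above shows that correcting only the denominator leaves unequal figures. Correcting only the window, with uptake 100/75/50/25, would print 11.8% × uptake = 11.8/8.8/5.9/2.9, a spurious fall.

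**The case against.** The strongest reply has four parts.

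- **Direction.** From the windows alone, a reader might infer that AE rates must rise with session number by construction. The documents do not support that. The long window belongs to each subject's own last session, which may be session 1, 2 or 3, and the Safety-population denominator pulls later optional sessions down. The direction depends on uptake and acute risk, neither of which is given. This limits the point to non-comparability.
- **Other outputs.** Table 3-46 is not the only session-level view of tolerability. SAP 2.5.2 and Tables 3-42 and 3-43 summarise diary reactions after each session over an equal 4-week diary. For injection reactions that is a fair common-window view. It does not cover nodules as a named item.
- **Late onset.** SAP 2.5.3 lists late-onset related AEs, and Table 3-47 gives time to onset from last treatment. Both help a careful reader, but neither removes those events from Table 3-46 or supplies person-time.
- **Status.** The SAP only summarises; no test or formal comparison between sessions is planned. Assignment to the most recent treatment is an inference for this table. Both are correct. The second is itself a gap, because without a stated rule two programmers could fill the table differently.

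**Conclusion.** The point stands as one of interpretability. If AEs are assigned to the most recent treatment, per-session percentages rest on 4-6 weeks of observation for a session followed by another and 34-52 weeks for a last session to Month 12 (86-104 to Month 24), over a denominator that includes subjects not injected at that session. With identical true risk, the figure for session 4 can be about twice that for session 1 (25.2% against 12.2%) or well under half of it (6.3% against 16.8%), depending on uptake.

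The windows follow from the documents. The percentages are illustrations under assumed rates and uptake; they ignore drop-out and take 5-week intervals. The statement about delayed nodules rests on the protocol's 1-14 month range set against a 4-6 week gap. The impact is confined to a descriptive safety table and its extension and combined versions. The primary analysis is unaffected.

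**What to change.** In SAP 2.5.3 and Table 3-46:

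1. State the rule that assigns a related AE to a session.
2. Under each session, count only related AEs with onset in one common, non-overlapping window. One option is days 0-27 after that session and before the next injection; this fits the minimum interval and the diary length, and avoids day 28, which can be the day of the next injection. The other is the SAP's existing 21-day cut. Use one threshold throughout, so that this table and the late-onset lists agree.
3. Use the number of subjects injected at that session as the denominator, and print it in each block.
4. Report related AEs with later onset in a separate block, not split by session, with the number of sessions received and person-time since the last injection.

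Cost: SAP wording and one table shell, with no new data. The small downside is that later-onset events are no longer attributed to a particular session.
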